## 6. SAFETY ANALYSIS

### 6.1 Safety Outcomes

For continuous safety parameters, summary statistics including number of participants, mean, median, standard deviation, minimum, and maximum will be obtained for baseline and Visit 4. Similar summary statistics will be obtained for the changes from baseline.

The outcome will be assessed for normality using Q-Q plots. If the outcome is normally distributed, then between group differences will be assessed by two-sample t-test. If the outcome is not normally distributed, then Wilcoxon rank sum test will be used. Within group differences will be assessed by paired t-test if the outcome is normally distributed and Wilcoxon signed rank test otherwise. P-values and 95% confidence intervals will be calculated.

Categorical safety parameters will be summarized as counts and percentages. The denominator for each percentage will be the number of subjects within the study group for that visit/week unless otherwise specified. Possible differences between groups will be assessed by using the two-tailed Chi-squared or Fisher's exact test, as appropriate.

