### 1.3 Schedule of Assessments

Procedures/assessments	Visit 1 Screen (Week -6)	Run-in Period Compliance Calls	Visit 2 Week 0	Visit 3 Week 6	Visit 4 Week 12
Informed consent	X				
Review inclusion/exclusion criteria	X		X		
Review medical history	X				
Review daily exercise habits	X				
Review concomitant therapies	X		X	X	X
Biometrics: Height*, weight, waist and hip circumference, heart rate, blood pressure, respiratory rate, and temperature	X		X	X	X
*only be measured at Visit 1					
Urine pregnancy test	X		X		
Physical examination			X		
Randomization			X		
CBC, Na, K, Cl, Fe, Mg, Ca, phosphate, HbA1c, fasting glucose, eGFR, creatinine, BUN, AST, ALT, GGT, ALP, TSH* and total bilirubin	X		X		X
*only be measured at Visit 1					
Blood Collection: lipid profile and fasting insulin	X		X		X
Urinalysis	X		X		X
DXA			X		X
BIA	X		X		
Stool Collection Kits Dispensed	X			X	
Stool Collection Kit Returned			X		X
Exercise Guideline Review	X	X	X	X	
Daily Bowel Habits Diary Dispensed	X		X	X	
Daily Bowel Habits Diary Returned			X	X	X
3DFR Dispensed	X		X	X	
3DFR Returned			X	X	X
Exercise Diary Dispensed	X		X	X	
Exercise Diary Returned			X	X	X
Subject Diary Dispensed	X		X	X	
Subject Diary Returned			X	X	X
Placebo Dispensed		X			
Placebo Returned			X		
IP Dispensed			X	X	

Procedures/assessments	Visit 1 Screen (Week -6)	Run-in Period Compliance Calls	Visit 2 Week 0	Visit 3 Week 6	Visit 4 Week 12
IP Returned				X	X
Compliance Calculated			X	X	X
Adverse Events		X	X	X	X

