## 9.5 Visit 3 (Week 6, 42 ± 3 days)

Participants will return to the clinic fasted for 12 hours, with the unused product, in addition to completed subject diaries, food records, daily bowel habits diaries and exercise diaries, for visit 3. Compliance calls will be made at fixed intervals.

Visit 3 assessments include:

1. Review concomitant therapies and adverse events
2. Collect unused investigational product; calculate compliance
3. Collect and review Subject Diary
4. Collect and review 3DFR
5. Collect and review Daily Bowel Habits Diary
6. Collect and review Exercise Diary
7. Seated resting blood pressure, heart rate, respiratory rate, and temperature measurements
8. Weight (BMI calculation), waist and hip circumference measurements (waist/hip circumference ratio)
9. Dispense investigational product and instruct participants on use
10. Dispense Subject Diary
11. Dispense 3DFR
12. Dispense Daily Bowel Habits Diary

Protocol 20BWHM:

A randomized, double-blind, placebo-controlled study to investigate the effects of a *Bifidobacterium breve* strain on fat loss in healthy adults

13. Dispense Exercise Diary
14. Dispense stool collection kits

The next visit will be scheduled for week 12 (EOS).

Reminders for participants prior to their next in-clinic visit:

1. Return to the clinic in a fasted state (12 hours or greater)
2. Maintain exercise intervention (20 min aerobic exercise x 3 days/week)
3. Abide by instructions for prescribed medications as per Section 7.3.1 and OTC medications, supplements, and food/drinks as per Section 7.3.2
4. Limit alcohol intake (<2 standard drinks per day or <10 per week)
5. Complete and return stool collections
6. Complete and return Daily Bowel Habits Diary
7. Complete and return 3DFR
8. Complete and return Exercise Diary
9. Complete and return Subject Diary
10. Return unused IP

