### **12.3.2 Safety**

For adverse events, a descriptive analysis will be given. Adverse events will be presented in a frequency table by category and treatment. Furthermore, description, frequency, severity, and causality will be reported for each adverse event.

Continuous safety parameters (e.g. hematology, clinical chemistry, heart rate and blood pressure, urine specific gravity) will be summarized using a table including mean, standard deviation, median, minimum value, and maximum value for each measurement point. These will be compared to normal clinical ranges and any abnormalities will be discussed.

Protocol 20BWHM:

A randomized, double-blind, placebo-controlled study to investigate the effects of a *Bifidobacterium breve* strain on fat loss in healthy adults

Categorical safety parameters (e.g. incidence of adverse events and urinalysis (microscopy, glucose, ketones, blood, protein, colour)) will be summarized as counts and percentages. The denominator for each percentage will be the number of subjects within the study group for that visit/week unless otherwise specified. Possible differences between groups will be assessed by using the two-tailed Chi-squared or Fisher's exact test, as appropriate.

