#### 2.2 Safety Outcomes

1. Incidence of pre-emergent and post-emergent adverse events
2. Vital signs (blood pressure (BP) and heart rate (HR)), respiratory rate, and temperature
3. Clinical chemistry (total bilirubin, creatinine, blood urea nitrogen (BUN), Na, K, Cl, Ca, Fe, Mg, phosphate, and estimated glomerular filtration rate (eGFR))
4. Hematology (white blood cell (WBC) count with differential (neutrophils, lymphocytes, monocytes, eosinophils, basophils), red blood cell (RBC) count, hemoglobin, hematocrit, platelet count, RBC indices (mean corpuscular volume (MCV), mean corpuscular hemoglobin (MCH), mean corpuscular hemoglobin concentration (MCHC), red cell distribution width (RDW), and mean platelet volume (MPV))
5. Urinalysis (microscopy, glucose, ketones, specific gravity, blood, protein, nitrite, leukocytes, colour, appearance urobilinogen/urine bilirubin, urine pH)

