## 7. MISSING DATA

All missing efficacy/effectiveness values analysis will be imputed using the most recent previously available value (LOCF, or “last-observation-carried-forward” imputation) or multiple imputation. No imputation techniques will be performed for missing values of safety variables.

Lab measurements that are below or above the threshold of quantification, will be imputed with that threshold value.

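### SAP 6.1 leaves the week-6 vital signs out of the safety summaries, although the protocol collects them and commits to summarising every measurement point

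*SAP*

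**What the plan says.** SAP 2.2 lists as a safety outcome "Vital signs (blood pressure (BP) and heart rate (HR)), respiratory rate, and temperature", with no restriction to week 12. SAP 6.1 then states that summary statistics for continuous safety parameters "will be obtained for baseline and Visit 4". It goes on: "Similar summary statistics will be obtained for the changes from baseline". That sentence names no visit.

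Protocol 12.3.2 is wider. Its sentence opens "Continuous safety parameters (e.g. hematology, clinical chemistry, heart rate and blood pressure, urine specific gravity", so two of the vital signs are named as examples. It promises a table giving the mean, standard deviation, "median, minimum value, and maximum value for each measurement point", followed by comparison with normal clinical ranges and discussion of abnormalities.

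On collection, the row of the Schedule of Assessments (Protocol 1.3) headed "Biometrics: Height*, weight, waist and hip circumference, heart rate, blood pressure, respiratory rate, and temperature" is marked at Visits 1, 2, 3 and 4, with only height confined to Visit 1. Protocol 9.5 lists among the Visit 3 procedures "Seated resting blood pressure, heart rate, respiratory rate, and temperature measurements".

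**The concern.** The protocol collects a set of safety measurements at week 6 and undertakes to report them. The SAP, which is the document the programmer will follow, names only two visits and leaves week 6 out. Visit 3 is the only clinic visit on treatment between baseline and the end of the study, so it is the only scheduled chance to see a change in vital signs that is present midway and gone by week 12.

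There is also a gap between population and table. SAP 3 admits to the Safety Population anyone who took product and has any safety information after randomisation. Someone whose only later vital signs come from Visit 3 belongs to that population, yet would have no entry in the post-baseline vital-sign tables.

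**Working it through.** No plan figure needs reproducing. The check compares the visits at which data are collected with the visits at which they are summarised.

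| | Visit 1 (screening) | Visit 2 (week 0) | Visit 3 (week 6) | Visit 4 (week 12) |
|---|---|---|---|---|
| Vital signs measured (Protocol 1.3, 9.1, 9.4 to 9.6) | yes | yes | yes | yes |
| Blood and urine safety tests measured (Protocol 1.3, 10.13) | yes | yes | no | yes |
| Vital-sign summaries under Protocol 12.3.2 | yes | yes | yes | yes |
| Vital-sign summaries under SAP 6.1 | no | yes | no | yes |

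1. **Post-baseline visits.** Vital signs have two, Visits 3 and 4. SAP 6.1 uses one, so 1/2 of the scheduled post-baseline vital-sign visits goes untabulated. The laboratory tests have one post-baseline visit, Visit 4, and SAP 6.1 uses it. The loss is therefore confined to four kinds of measurement: blood pressure, heart rate, respiratory rate and temperature.

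2. **Screening.** SAP 6.1 also omits Visit 1, which a literal reading of Protocol 12.3.2 would include. Those values precede baseline, so this matters less and is not pressed here.

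3. **Could the change-from-baseline sentence bring week 6 back?** It follows directly on a sentence that yields only Visit 4 after baseline. Even read generously, it would give week-6 changes without week-6 values.

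4. **Is the two-visit wording shorthand for every visit?** The rest of the SAP suggests not. SAP 5.2 asks for secondary-outcome summaries at each visit and for every available change to later visits. SAP 5.1 names two visits for the primary outcome, where DXA is in fact done at only two. The wording of 6.1 follows the two-visit pattern, which is right for the laboratory data and wrong for vital signs.

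5. **Does another part of the SAP cover it?** SAP 6.2 covers adverse events, and the categorical paragraph of 6.1 uses visit-specific denominators. Neither summarises a continuous vital sign at week 6.

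6. **How many people have only a Visit 3 reading after baseline?** Protocol 12.1 plans 50 per group with 40 completers, so 2 × (50 − 40) = 20 non-completers. If attrition is as planned, the number affected lies between 0 and 20. It depends on how many leave between Visits 3 and 4 and how many of those have no later evaluation. The documents give neither, so no estimate within that range is defensible.

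**The case against.** The mismatch in visits is hard to dispute. The case on the other side is that little follows from it, and much of that case stands.

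- **Withdrawal provisions.** A reader might infer that anyone who leaves after week 6 contributes no post-baseline vital sign. The documents do not support that as the general case. Protocol 7.5 asks, where possible, for the end-of-treatment evaluations to be done at withdrawal, and Protocol 9.6 includes vital signs among those. Protocol 11.2.2 keeps some participants who come off treatment, including those who withdraw by their own choice, attending the remaining visits. What remains is that these evaluations will not always happen, and that the SAP does not say whether a reading taken at withdrawal is tabulated as Visit 4.

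- **Completers only.** A reader might also infer that the safety tables would describe only people who reached week 12. That is too broad. Adverse-event reporting is not limited to completers, and entry to the Safety Population does not require a Visit 4.

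- **Transient effects.** It is tempting to say that a mid-study change could not be seen at all. Adverse events are reviewed at Visit 3, and the definition in Protocol 11.1.1 takes in unfavourable signs, so a clinically relevant change should be captured there. What would be lost is the group-level picture: a shift in means or spread that nobody records as an event.

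- **No imputation.** SAP 7 says "No imputation techniques will be performed for missing values of safety variables", and Protocol 12.3 has the same rule. The rule is reasonable and does not cause this gap. The week-6 readings are not missing; they are left out of the tables.

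**Conclusion.** The inconsistency is real and limited in size. Following SAP 6.1 to the letter leaves one of two scheduled post-baseline vital-sign visits out of the safety summaries, contrary to Protocol 12.3.2. No post-baseline laboratory or adverse-event data are lost.

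The count of one visit in two rests only on the visit schedule. The further statement, that some participants would drop out of the post-baseline vital-sign tables altogether, assumes that at least one person leaves after Visit 3 without a later reading. How many is unknown. A figure such as half of the planned non-completers would rest on an assumed timing of dropout that the documents do not give, and would ignore the withdrawal provisions. Nor do the documents show that early leavers are more likely to have had abnormal vital signs; the point stands without that argument.

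This is a low-priority correction. It is worth making because the data will already be in hand and the protocol already promises the table.

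**What to change.** In SAP 6.1, replace the words naming baseline and Visit 4 with:

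*for each visit at which the parameter is measured (baseline, Visit 3 for vital signs, and Visit 4), with change from baseline at each post-baseline visit.*

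The cost is one phrase in the SAP and one extra column in the vital-sign tables. No procedure, sample or visit changes. SAP 6.1 also attaches between-group and within-group tests to continuous safety parameters without naming a visit, so the sponsor should say whether those extend to week 6. Protocol 12.3.2 promises only summaries for these parameters, so descriptive week-6 columns are enough to meet it.

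A table of last post-baseline values, or a row pooling Visit 4 with early-withdrawal readings, is not needed to match the protocol, and the pooled row would mix different lengths of exposure. It would still help to state how a reading taken at withdrawal is assigned to a visit.

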### 6.2 Adverse Events

A descriptive analysis will be provided for pre-emergent and post-emergent AEs. AEs will be presented along with the system organ class, preferred term, and lower-level term. Furthermore, description, frequency, severity, and relationship to study product will be reported for each AE.

## 7. MISSING DATA

All missing efficacy/effectiveness values analysis will be imputed using the most recent previously available value (LOCF, or “last-observation-carried-forward” imputation) or multiple imputation. No imputation techniques will be performed for missing values of safety variables.

Lab measurements that are below or above the threshold of quantification, will be imputed with that threshold value.

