## **10.8 Dual-Energy X-Ray Absorptiometry (DXA) Scan**

The Dual-Energy X-Ray Absorptiometry Scan will be conducted at KGK clinic (London, ON) at visits 2 (week 0), and 4 (week 12) by trained technicians. Body tissue density will be measured by a form of X-ray radiation and converted into body fat and muscle mass percentage for assessment. Prior to the day of the DXA assessment, the coordinators will remind the participants to limit the amount of water and food consumption accordingly. A full body composition DXA scan will expose the participant to a total dose of <10uSV, depending on the size of the participant. This amount is less than a person is exposed to on an east to west coast flight within the USA and similar to the normal background radiation received over the course of a single day level (23, 24).

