Baseline values for continuous variables will be tested for between-group differences using the independent Student's t-test. Within-group differences will be assessed using the Student's paired t-test or, in the case of intractable non-normality, the Wilcoxon sign rank test. The frequency of BMs will be calculated as the average number of BMs per day over the 7 days prior to baseline and 7 days prior to week 6 and week 12.

For categorical variables, counts and percentages will be presented. The denominator for each percentage will be the number of subjects within the study group for that visit/week unless otherwise specified. Possible differences between groups will be assessed by using the two-tailed Chi-squared or Fisher's exact test, as appropriate.

Microbiota analysis will be performed at Morinaga Milk Co., Ltd. The subgroups will be determined based on the similarity of microbiota composition by hierarchical clustering. These subgroups will be defined before analyzing week 12 data.

All missing efficacy/effectiveness values analysis will be imputed using the most recent previously-available value (LOCF, or "last-observation-carried-forward" imputation) or multiple imputation. No imputation will be performed for missing values of safety variables.

All statistical analysis will be completed using R Statistical Software version 3.5.3 (R Core Team, 2019) for Microsoft Windows or SAS software, Copyright © 2019 SAS Institute Inc. SAS and all other SAS Institute Inc. product or service names are registered trademarks or trademarks of SAS Institute Inc., Cary, NC, USA.

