### 3. STUDY POPULATION

A total of three populations are defined for all summaries and analyses. Subjects who satisfy the inclusion/exclusion criteria will be classified in the designated populations:

- **The Safety Population** will consist of all participants who received any amount of either product and on whom any post-randomization safety information is available.
- **The Intent-to-Treat (ITT) Population** will consist of all participants who received either product and on whom any post-randomization efficacy information is available.
- **The Per Protocol (PP) Population** will consist of all participants who consumed at least 80% of treatment or placebo doses, do not have any major protocol violations and complete all study visits and procedures connected with measurement of the primary variable.

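### The plan leaves the choice between LOCF and multiple imputation open, and LOCF would score an ITT participant with no second DXA scan as exactly zero fat change

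*SAP*

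**What the plan says.** SAP section 7: "All missing efficacy/effectiveness values analysis will be imputed using the most recent previously available value (LOCF". The sentence then offers an alternative: "or multiple imputation. No imputation techniques will be performed for missing values of safety variables". Protocol section 12.3 has the same pair, opening "All missing efficacy/effectiveness values analysis will be imputed using the most recent previously-available value (LOCF". Neither document says which method is primary, what decides between them, what the imputation model contains, or whether one is a sensitivity analysis for the other.

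Three other provisions determine what LOCF does here:

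- **DXA timing.** Protocol section 10.8 schedules scans "at visits 2 (week 0), and 4 (week 12) by trained technicians", and the schedule in section 1.3 agrees. Blood is likewise drawn after randomization only at week 12.
- **Week 6.** Protocol section 9.5 collects "Weight (BMI calculation), waist and hip circumference measurements (waist/hip circumference ratio") and the bowel diary, but no DXA.
- **Analysis sets.** SAP section 3 says "A total of three populations are defined for all summaries and analyses" without ranking them. ITT is "all participants who received either product and on whom any post-randomization efficacy information is available". The per-protocol set requires participants to "complete all study visits and procedures connected with measurement of the primary variable".

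**The concern.** A participant who attends week 6 and has no later scan qualifies for ITT through weight, waist, hip or bowel data. The only DXA value to carry forward is the baseline scan, so the week-12 change is zero by construction. The same happens to lipids, glycemic markers and liver markers when the week-12 blood draw is missing.

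The plan expects 20% attrition. If the product works, scored zeros pull the estimated difference toward zero. If both arms lose fat and dropout differs by arm, zeros can produce a difference where none exists. Because the method is not fixed in advance, two analyses that both follow the plan can also reach different conclusions on significance.

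**Working it through.** **Inputs from protocol section 12.1:** 50 randomized and 40 completers per arm, SD of change 1.19 percentage points, detectable difference 0.76, two-sided 5%, 80% power, 20% attrition.

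**Assumptions (not in the documents):** the placebo mean loss; the split of dropout between arms; the share q of dropouts who have week-6 data but no second scan, with the remaining dropouts taken as outside ITT; baseline correlated -0.2 with change; dropout random within arm.

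**Step 1, the plan's own figure.** A two-sample t-test with 40 per arm, difference 0.76 and SD 1.19 has power 80.5% (80.3% for 0.79 kg with SD 1.24). 40/(1 - 0.20) = 50. The sample size reproduces, but it describes an analysis of completers, not one that adds imputed zeros.

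**Step 2, expected LOCF estimate.** With dropout p, the zeroed fraction of an arm's ITT set is f = pq/(1 - p + pq), and the expected difference is 0.76 x (1 - f).

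- q = 0.25: f = 0.05/0.85 = 0.059, giving 0.76 x 40/42.5 = 0.715 (6% shrinkage)
- q = 0.50: f = 0.10/0.90 = 0.111, giving 0.76 x 40/45 = 0.676 (11%)
- q = 1.00: f = 0.20, giving 0.76 x 40/50 = 0.608 (20%)

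**Step 3, power and coverage.** ANCOVA, 20,000 simulated trials per scenario, true difference 0.76, 20% dropout in each arm:

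| Share zeroed | Power, no placebo loss | Power, 0.5-point loss | Coverage |
|---|---|---|---|
| Quarter | 81% | 80% | 94-95% |
| Half | 81% | 79% | 94% |
| All (upper bound) | 81% | 77% | 89% |

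Complete-case ANCOVA has power 81-82%. At a 1.0-point loss LOCF power is 78%, 75% and 71%. That is a stress case: the baseline scan follows a 4-week run-in on the same exercise plus placebo, and participants losing more than 0.7 kg per week in that period are withdrawn (protocol sections 9.2 and 9.4).

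**Step 4, no true effect.** With equal dropout LOCF is unbiased and rejects in about 5% of trials. With unequal dropout the false difference is loss x (difference in f between arms). For 10% against 30%, q = 0.5 and a 0.5-point loss: 0.5 x (0.15/0.85 - 0.05/0.95) = 0.062.

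| Dropout and loss | False difference (quarter, half, all zeroed) | Rejection |
|---|---|---|
| 15% vs 25%, 0.5 points | 0.017, 0.031, 0.05 | 5.0%, 5.3%, 5.6% |
| 10% vs 30%, 0.5 points | 0.035, 0.062, 0.10 | 5.0%, 5.8%, 7.5% |
| 10% vs 30%, 1.0 point | 0.070, 0.124, 0.20 | 6.0%, 8.0%, 14.7% |

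**Step 5, does the choice matter?** Multiple imputation used 20 imputations from arm, baseline DXA, sex, and weight and waist at weeks 0 and 6. Week-6 weight and waist changes were assumed to correlate 0.6 and 0.4 with fat change. With a true 0.76 and a 0.5-point loss it gives an estimate of 0.76-0.77, 95% coverage and power of 83-84%; complete-case power on the same trials is 82-83%. LOCF and multiple imputation disagree on significance in about 6%, 8% and 11% of trials for a quarter, half and all zeroed. Random dropout favours imputation and complete-case analysis by construction.

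**The case against.** **The realistic harm is small.** In the central scenarios power is 79-81% against a target of 80%, and coverage is near nominal. This stands, and it sets the size of the point. A reader might infer that the whole 20% would be scored zero. The documents do not support that. Protocol section 7.5 asks for end-of-treatment evaluations at withdrawal if possible. Section 11.2.2 keeps participants who withdraw themselves in the study for the remaining visits, though it does not say whether those include DXA. A participant who leaves before week 6 with no exit assessment generally has no efficacy data and falls outside ITT.

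**A reader might infer an inflated false-positive rate.** That needs unequal dropout plus fat loss in both arms, and nothing in the documents predicts unequal dropout: the placebo has the same non-medical ingredients as the product. If both arms truly drop out at 20%, a gap of 10 or more participants out of 50 arises in about 1.7% of trials.

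**A reader might infer that the analyst will pick the favourable method.** Taking the smaller p-value would raise rejection to only 5.7-6.6% under equal dropout, and protocol section 15.3 sends the statistician a blinded database. The documents give no ground for assuming selection; the defect is that the method is not fixed.

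**Naming either method would settle the choice, and imputation has a bias of its own.** The first part is true of the open choice but leaves the artificial zero in place if LOCF is named. The second part stands. Protocol section 10.12 withdraws participants below 70% exercise compliance for two consecutive weeks, and two of three sessions is 67%. Section 7.5 withdraws users of prohibited medication. Such dropout may be related to outcome. If five per arm reverted to zero change, the true all-participant difference would be 0.76 x 40/45 = 0.68; imputation under missing at random would give about 0.76, some 12% too high, and LOCF would be right. A sensitivity analysis therefore has to be required.

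**Multiple imputation gains little over complete-case ANCOVA.** Also true in these runs. The reasons to name it are that the plan already permits it and that it uses the week-6 data.

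**Conclusion.** The point holds as a should-fix matter of modest expected size. The missing-data method for the primary outcome is not fixed, and one of the two permitted methods assigns an artificial value of zero change to ITT participants with no second scan. With 20% dropout per arm, a quarter to half of dropouts zeroed and a placebo loss of 0 to 0.5 points, the estimate shrinks by 6-11% and power falls by about 0-3 points. The loss and the share zeroed are assumptions, and the number actually exposed cannot be derived from the documents.

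Two limits apply. The per-protocol set is unaffected, and since neither document says whether ITT or per-protocol is primary for this endpoint, the effect on the headline result depends on that unstated choice. A reader might also infer that LOCF always precedes the mixed model for outcomes #2 and #6; it does so only if LOCF is the method chosen. The difference between the SAP's ANCOVA and the protocol's mixed model for outcomes #1 and #3 to #5 is a separate matter.

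**What to change.** In protocol section 12.3 and SAP section 7:

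1. Remove LOCF as a primary option. Name multiple imputation under missing at random as the single primary method for the week-12 DXA outcome in the ITT set as now defined. Use arm, baseline DXA, sex, and weight and waist at weeks 0 and 6, imputing missing week-6 values in the same model. State the number of imputations and the pooling rule, and which data the additional t-tests and rank tests in SAP section 5.1 use.
2. Use the same approach for the other outcomes analysed only at week 12.
3. For outcomes #2 and #6, if LOCF would otherwise have been used, fit the SAP's mixed model to the observed data instead.
4. Require a delta-adjusted or reference-based sensitivity analysis for the primary outcome.
5. State in advance how a scan taken at early withdrawal is used. This is the sponsor's estimand decision.

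**Cost:** wording and modest programming, with no new data or visits and no change to the ITT definition. The interval is somewhat wider. At a 0.5-point loss the mean 95% interval width is 1.04, 1.03 and 1.02 points with multiple imputation, against 1.00, 0.96 and 0.89 with LOCF, for a quarter, half and all zeroed. With half zeroed, the imputation width runs from 1.06 to 1.01 as the assumed correlation of week-6 weight change with fat change goes from 0.3 to 0.8. The narrower LOCF interval is not a real gain, because its coverage drops to 89% when all dropouts are zeroed.
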